4.4. End of Study Definition

The end of the study is defined as the date of the last visit of the last participant in the study.

A participant is considered to have completed the study if he/she has completed all periods of the study, including the last visit.

5. STUDY POPULATION

This study can fulfill its objectives only if appropriate participants are enrolled. The following eligibility criteria are designed to select participants for whom participation in the study is considered appropriate. All relevant medical and nonmedical conditions should be taken into consideration when deciding whether a particular participant is suitable for this protocol.

Prospective approval of protocol deviations to recruitment and enrollment criteria, also known as protocol waivers or exemptions, is not permitted.

5.1. Inclusion Criteria

Participants are eligible to be included in the study only if all of the following criteria apply:

Age and Sex:

1. Male and female participants must be 20 to 55 years of age, inclusive, at the time of signing the ICD.
 - Refer to [Appendix 4](#) for reproductive criteria for male ([Section 10.4.1](#)) and female ([Section 10.4.2](#)) participants.

Type of Participant and Disease Characteristics:

2. Participants must have 4 biologically Japanese grandparents born in Japan.
3. Male and female participants who are overtly healthy as determined by medical evaluation including medical history, physical examination, laboratory tests, and 12-lead ECG.
4. Participants who are willing and able to comply with all scheduled visits, treatment plan, laboratory tests, lifestyle considerations, and other study procedures.

Weight:

5. BMI of 17.5 to 25 kg/m²; and a total body weight >50 kg (110 lb).

Informed Consent:

6. Capable of giving signed informed consent as described in [Appendix 1](#), which includes compliance with the requirements and restrictions listed in the ICD and in this protocol.

5.2. Exclusion Criteria

Participants are excluded from the study if any of the following criteria apply:

Medical Conditions:

1. Evidence or history of clinically significant hematological, renal, endocrine, pulmonary, gastrointestinal, cardiovascular, hepatic, psychiatric, neurological, or allergic disease (including drug allergies, but excluding untreated, asymptomatic, seasonal allergies at the time of dosing).
2. History of HIV infection, hepatitis C or syphilis; positive testing for HIV, HCVAb or syphilis at screening.
3. Infection with HBV as defined in [Section 8.2.6.1](#).
4. Clinically significant abnormality, including but not limited to current, active TB or previous inactive TB, general infections, heart failure or malignancy, on chest X-ray performed at screening or within 12 weeks of screening.
5. History of autoimmune disorders.
6. History of allergic or anaphylactic reaction to a therapeutic drug or any components in the study intervention.
7. Participants with clinically significant infections, based on which the investigator judges that the participant should not be enrolled in the study, within 28 days prior to the screening visit.
8. Participants with a fever, based on which the investigator judges that the participant should not be enrolled in the study, within the last 7 days prior to dosing.
9. Participants who have evidence of TB infection as defined in [Section 8.2.7](#).
 - Participants who have been treated or are currently being treated for active or latent TB infection are to be excluded.
 - Participants with a history of either untreated or inadequately treated latent or active TB infection are to be excluded.

10. Other medical or psychiatric condition including recent (within the past year) or active suicidal ideation/behavior or laboratory abnormality or other conditions or situations related to COVID-19 pandemic (eg, Contact with positive case, residence, or travel to an area with high incidence) that may increase the risk of study participation or, in the investigator's judgment, make the participant inappropriate for the study.

Prior/Concomitant Therapy:

11. Use of prescription or nonprescription drugs and dietary and herbal supplements within 7 days or 5 half-lives (whichever is longer) prior to the first dose of study intervention. (Refer to [Section 6.8](#) for additional details).
12. Recent exposure to any live or attenuated live virus vaccines within 6 weeks of admission to CRU.
 - The use of COVID-19 vaccines (except for live or attenuated live virus vaccines) are allowed before 14 days prior to Day 1 or after discharge from CRU.

Prior/Concurrent Clinical Study Experience:

13. Participants who have received PF-06823859 or any other IFN α or IFN β therapy at any time in the past.
14. Previous administration with an investigational drug within 4 months (180 days for biologics) or 5 half-lives preceding the first dose of study intervention used in this study (whichever is longer).

Diagnostic Assessments:

15. A positive urine drug test.
16. Screening supine BP \geq 140 mm Hg (systolic) or \geq 90 mm Hg (diastolic), following at least 5 minutes of supine rest. If BP is \geq 140 mm Hg (systolic) or \geq 90 mm Hg (diastolic), the BP should be repeated 2 more times and the average of the 3 BP values should be used to determine the participant's eligibility.
17. Screening PR $>$ 100 bpm. If the PR is greater than 100 bpm, the PR should be repeated 2 more times and the average of the 3 PR values should be used to determine the participant's eligibility.
18. Baseline standard 12-lead ECG that demonstrates clinically relevant abnormalities that may affect participant safety or interpretation of study results (eg, baseline QTc interval $>$ 450 msec, complete LBBB, signs of an acute or indeterminate-age myocardial infarction, ST-T interval changes suggestive of myocardial ischemia, second- or third-degree AV block, or serious bradyarrhythmias or tachyarrhythmias).

If the baseline uncorrected QT interval is >450 msec, this interval should be rate-corrected using the Fridericia method and the resulting QTcF should be used for decision making and reporting. If QTc exceeds 450 msec, or QRS exceeds 120 msec, the ECG should be repeated 2 more times and the average of the 3 QTc or QRS values should be used to determine the participant's eligibility. Computer-interpreted ECGs should be overread by a physician experienced in reading ECGs before excluding a participant.

19. Participants with **ANY** of the following abnormalities in clinical laboratory tests at screening, as assessed by the study-specific laboratory and confirmed by a single repeat test, if deemed necessary:
 - AST **or** ALT level $\geq 1.5 \times$ ULN;
 - Total bilirubin level $\geq 1.5 \times$ ULN; participants with a history of Gilbert's syndrome may have direct bilirubin measured and would be eligible for this study provided the direct bilirubin level is \leq ULN.
20. A positive COVID-19 test by PCR at screening.

Other Exclusions:

21. History of alcohol abuse or binge drinking and/or any other illicit drug use or dependence within 6 months of screening. Binge drinking is defined as a pattern of 5 (male) and 4 (female) or more alcoholic drinks in about 2 hours. As a general rule, alcohol intake should not exceed 14 units per week (1 unit = 8 ounces (240 mL) beer, 1 ounce (30 mL) of 40% spirit or 3 ounces (90 mL) of wine).
22. Blood donation (excluding plasma donations) of approximately ≥ 400 mL within 3 months or ≥ 200 mL within a month prior to dosing. Additionally, approximately ≥ 400 mL within 4 months for female participants.
23. History of sensitivity to heparin or heparin-induced thrombocytopenia **only if** heparin is planned to flush intravenous catheters.
24. History of substance abuse within 12 months of the screening visit.
25. Pregnant females; breastfeeding females.
26. Unwilling or unable to comply with the criteria in the Lifestyle Considerations section of this protocol.
27. Investigator site staff or Pfizer employees directly involved in the conduct of the study, site staff otherwise supervised by the investigator, and their respective family members.

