2.2.2.1. Safety

Data from Study C0251001 suggests that PF-06823859 was generally well tolerated and safe when given up to 2000 mg as single IV dose and up to 1800 mg given 600 mg IV Q2W × 3. The most common AE was upper respiratory tract infection, likely due to viral infection. No serious AE or death occurred during the study.

During the SAD period, all TEAEs reported were mild in severity. During the MAD period, while the majority of the TEAEs were mild in severity, 4 TEAEs were moderate in severity: 2 TEAEs (abdominal pain upper and headache) in the placebo SC × 3 doses treatment group, 1 TEAE (upper respiratory tract infection) in the PF-06823859 300 mg SC × 3 doses treatment group and 1 TEAE (sinusitis) in the PF-06823859 600 mg IV (Q4W) × 2 doses treatment group, none of which were considered by the investigator as treatment related.

One participant experienced a mild localized erythema with induration and tenderness after each of the 100 mg SC dosing with PF-06823859 administered Q2W for a total of 3 doses, but no signs or symptoms of a systemic reaction. These local reactions resolved without further intervention within a few days. This participant also had treatment-induced ADA, which had returned to baseline at the time of discharge ([Section 2.2.2.3](#)).

Overall, there was no apparent difference in the total rate of AEs between the participants treated with PF-06823859 compared to placebo and no apparent dose relationship with the doses of PF-06823859. However, the rate of mild upper respiratory tract infection appears to be higher in participants treated with PF-06823859.

There were no clinically significant observations in ECG, vital signs or laboratory abnormalities.

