2.2.2.2. Pharmacokinetics

Following single IV administration of 30 mg to 2000 mg doses, PF-06823859 demonstrated a bi-phasic PK profile with a terminal half-life ranging from 22.73 to 29.08 days, slow CL (0.005953 to 0.006817 L/h) and small volume of distribution (4.828 to 6.013 L), all attributes

of a typical IgG1 molecule. Further, T_{max} occurred around 1 hour after the end of the IV infusion, C_{max} ranged from 10.81 to 708.3 $\mu\text{g}/\text{mL}$, and AUC_{inf} ranged from 5042 to 322,100 $\mu\text{g} \cdot \text{h}/\text{mL}$. Both C_{max} and AUC_{inf} showed dose proportional increases across the 30 mg to 2000 mg dose range.

Following multiple IV administration of PF-06823859 at either 600 mg dosing Q2W for a total of 3 doses or 600 mg dosing Q4W for a total of 2 doses, C_{max} and C_{av} after last dose were 284.9 $\mu\text{g}/\text{mL}$ and 181.6 $\mu\text{g}/\text{mL}$ for 600 mg IV Q2W and 259.5 $\mu\text{g}/\text{mL}$ and 109.6 $\mu\text{g}/\text{mL}$ for 600 mg IV Q4W. R_{ac} (based on AUC_{τ}) following 600 mg IV Q2W and 600 mg IV Q4W dosing on Day 29 were 1.893 and 1.407, respectively. R_{ac} , C_{max} (based on C_{max}) was similar with a mean ratio of 1.079 for 600 mg IV Q2W dosing regimen and 1.298 for 600 mg IV Q4W dosing regimen.

Following multiple SC administration of PF-06823859 at either 100 mg or 300 mg dosing Q2W for a total of 3 doses, C_{max} was reached moderately slow with median T_{max} of 96 hours following the first SC dose on Day 1, and slightly earlier at 48 hours after the second dose (Day 15) and the third dose (Day 29), respectively. In addition, C_{max} and C_{av} after last dose were 19.49 $\mu\text{g}/\text{mL}$ and 18.11 $\mu\text{g}/\text{mL}$ for 100 mg SC and 62.92 $\mu\text{g}/\text{mL}$ and 54.26 $\mu\text{g}/\text{mL}$ for 300 mg SC. R_{ac} (based on AUC_{τ}) following 100 mg SC Q2W and 300 mg SC Q2W dosing on Day 29 were 2.376 and 2.499, respectively. R_{ac} , C_{max} (based on C_{max}) was similar with a mean ratio of 2.063 for 100 mg SC Q2W dosing regimen and 2.294 for 300 mg SC Q2W dosing regimen.

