2.3. Benefit/Risk Assessment

A single-dose of PF-06823859 is not expected to provide any clinical benefit to healthy participants. This study is designed primarily to generate safety, tolerability, immunogenicity and PK data for further clinical development.

Nonclinical data to date (Section 2.2.1) has not identified any risk to reproductive organs in sexually mature cynomolgus monkeys, the pharmacologically relevant species. Given that an ePPND study will be conducted later in development, this protocol that allows enrollment of WOCBP has requirements for pregnancy testing (WOCBP only) and use of contraceptives to mitigate unintended exposures.

There is a theoretical risk that alterations in bone may occur based on published observations of osteopenia in mice genetically deficient in IFN β .⁴ The potential for bone effects was assessed in the 3-month GLP toxicity study in sexually mature cynomolgus monkeys, and there were no microscopic findings in bone, nor alterations in circulating bone-related biomarkers. However, the potential for bone effects in developing/growing bones has not

been specifically assessed in growing animals. This risk is considered to be low given the lack of observed effects in the GLP toxicity study as well as the limited duration of total exposure to PF-06823859 in this study. While appropriate risk mitigation has been employed, possible risks will be communicated to study participants in the ICD.

There is a potential risk of increased susceptibility to viral infections with IFN β blockade as with any antagonist of Type 1 interferon signaling (eg, anti-IFNAR1, anti-IFN α , JAK inhibitors). Viral monitoring will be conducted as a precautionary measure to ensure participant safety. Furthermore, during the pandemic, study participants could be infected with the SARS-CoV-2 during study participation. This could lead to increased health risk for this participant and others in the study. Thus, participants must undergo COVID-19 specific assessments according to the [SoA](#).

More detailed information about the known and expected benefits and risks and reasonably expected adverse events of PF-06823859 may be found in the IB, which is the SRSD for this study.

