6.8. Concomitant Therapy

Use of prescription or nonprescription drugs and dietary and herbal supplements are prohibited within 7 days or 5 half-lives (whichever is longer) prior to the first dose of study intervention. Limited use of nonprescription medications that are not believed to affect participant safety or the overall results of the study may be permitted on a case-by-case basis following approval by the sponsor. Acetaminophen/paracetamol may be used at doses of ≤ 1 g/day. Ibuprofen may be used at doses of ≤ 1.6 g/day.

Hormonal contraceptives that meet the requirements of this study are allowed to be used in participants who are WOCBP (see [Appendix 4](#)).

All concomitant treatments taken during the study must be recorded with indication, daily dose, and start and stop dates of administration. All participants will be questioned about concomitant treatment at each clinic visit.

Treatments taken within 28 days before the first dose of study intervention will be documented as a prior treatment. Treatments taken after the first dose of study intervention will be documented as concomitant treatments.

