10.4. Appendix 4: Contraceptive and Barrier Guidance

10.4.1. Male Participant Reproductive Inclusion Criteria

Male participants are eligible to participate if they agree to the following requirements during the intervention period and for at least 150 calendar days after the last dose of study intervention, which corresponds to the time needed to eliminate reproductive safety risk of the study intervention(s):

- Refrain from donating sperm.

PLUS either:

- Be abstinent from heterosexual intercourse with a female of childbearing potential as their preferred and usual lifestyle (abstinent on a long-term and persistent basis) and agree to remain abstinent.

OR

- Must agree to use contraception/barrier as detailed below:
 - Agree to use a male condom and should also be advised of the benefit for a female partner to use a highly effective method of contraception as a condom may break or leak when having sexual intercourse with a woman of childbearing potential who is not currently pregnant.

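### Nothing in the protocol bars a non-COVID live vaccine between CRU discharge and Day 157, while drug exposure is still substantial

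*Protocol*

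**What the plan says.** Live vaccines appear in one place in the protocol, Section 5.2, criterion 12, which excludes people with "Recent exposure to any live or attenuated live virus vaccines within 6 weeks of admission to CRU". The sub-bullet beneath it adds that "COVID-19 vaccines (except for live or attenuated live virus vaccines) are allowed before 14 days prior to Day 1", and the same sentence allows them again after discharge. Live COVID-19 vaccines are left out of that permission.

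Section 6.8 (Concomitant Therapy) ties its prohibition to initial dosing: "Use of prescription or nonprescription drugs and dietary and herbal supplements are prohibited within 7 days or 5 half-lives (whichever is longer) prior to" that point. It allows some nonprescription medication case by case with sponsor approval, sets dose limits for acetaminophen and ibuprofen, and allows qualifying hormonal contraceptives. Treatments taken after dosing are to be recorded. Section 5.3 (Lifestyle Considerations) covers diet, caffeine, alcohol, tobacco, exercise and contraception. The SAP does not address vaccination.

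On the risk itself, Section 2.3 says "There is a potential risk of increased susceptibility to viral infections with IFN"-beta blockade. Section 2.2.2.1 reports from the earlier healthy-volunteer study that "the rate of mild upper respiratory tract infection appears to be higher in participants treated with PF-06823859". For contraception, Section 10.4.1 sets a restriction that lasts "for at least 150 calendar days after the last dose of study intervention, which corresponds to the time needed to eliminate reproductive safety risk", and Section 10.4.2 uses the same 150 days for women.

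**The concern.** The one live-vaccine rule protects the period before the participant has any drug on board and says nothing about the period after. A live vaccine five weeks before admission excludes a volunteer. The same vaccine on Day 6, squarely within drug exposure, is not addressed.

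Participants are healthy and gain no benefit from the drug. A live vaccine introduces a replicating virus while the infection risk named in the protocol applies. The exposure is foreseeable and avoidable, and once it has happened no analysis can repair it. The protocol already sets a post-dose window for another exposure-related risk, so leaving this one open looks like an oversight rather than a decision.

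**Working it through.** **1. Does any text cover dosing to Day 157?**

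| Place | What it governs | Bans a non-COVID live vaccine after dosing? |
|---|---|---|
| 5.2, criterion 12 | Recent exposure, judged at entry | No, it looks back only |
| 5.2, sub-bullet | COVID-19 vaccines | No, other vaccines are not mentioned |
| 5.3 | Lifestyle restrictions | No, vaccines are not mentioned |
| 6.8, first sentence | Drugs before the first dose | No |
| 6.8, limited-use sentence | Nonprescription medication | No, vaccines are not mentioned |
| 6.8, last paragraph | Recording of later treatments | No, it documents them |

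**2. Are the pharmacokinetic inputs consistent?** Section 2.2.2.2 gives a "terminal half-life ranging from 22.73 to 29.08 days", clearance (CL) 0.005953 to 0.006817 L/h and volume 4.828 to 6.013 L. It gives Cmax from 10.81 µg/mL at 30 mg to 708.3 µg/mL at 2000 mg, and AUCinf from 5042 to 322,100 µg·h/mL.

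- CL = dose/AUCinf: 30/5042 = 0.00595 L/h and 2000/322,100 = 0.00621 L/h. The first agrees with the stated lower limit and the second lies within the stated range.
- Half-life = ln2 × V/CL over the four corner pairings: 20.5 to 29.2 days, which brackets the stated range. Per-dose pairings are not given, so an exact match cannot be tested.

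**3. Fraction left by half-life decay, 0.5^(t/half-life).**

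| Days after dose | Half-life 22.73 d | Half-life 29.08 d |
|---|---|---|
| 28 | 43% | 51% |
| 42 (six weeks) | 28% | 37% |
| 70 | 12% | 19% |
| 150 | 1.0% | 2.8% |

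The profile is bi-phasic, so these are not fractions of Cmax. Concentrations need the next step.

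**4. Concentrations, by three routes.**

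- *Terminal phase.* C(t)/dose = (λ/CL) × exp(−λt), with λ = ln2/half-life, over all pairs of CL and half-life limits. This treats the whole profile as terminal phase, so it runs low early and high late.
  - At 96 h (discharge): 0.132 to 0.189 µg/mL per mg, that is 40 to 57 µg/mL after 300 mg and 119 to 170 µg/mL after 900 mg. Cmax per mg is 10.81/30 = 0.360 and 708.3/2000 = 0.354, so this is 37 to 53% of Cmax.
  - At 1008 h (six weeks): 0.0518 to 0.0613 µg/mL per mg, that is 47 to 55 µg/mL after 900 mg.
- *Two compartments.* Central volume is about 2.80 L (dose/Cmax) and Vss 4.828 to 6.013 L. Inter-compartment clearance is **assumed** at 0.005 to 0.03 L/h, keeping only sets whose half-life falls in the stated range. Result: about 45 to 70% of Cmax at 96 h, and 34 to 52 µg/mL at six weeks after 900 mg.
- *Observed accumulation.* After 600 mg IV Q4W, the Cmax of 259.5 µg/mL and accumulation ratio of 1.298 imply 259.5 − 259.5/1.298 = 59.6 µg/mL left at Day 29 from the first dose, about 30% of its Cmax. Scaled to 900 mg: 59.6 × 1.5 = 89 µg/mL at Day 29. Decaying that for 14 more days (× 0.65 to 0.72) gives 58 to 64 µg/mL at six weeks.

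For scale, Section 2.2.2.2 reports an average concentration of 54.26 µg/mL on repeated 300 mg SC Q2W. The first two routes give 33.7/54.26 = 62% to 55.2/54.26 = 102% of that. The third is somewhat higher.

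**5. How long would a ban need to run?** Five half-lives are 5 × 22.73 = 114 to 5 × 29.08 = 145 days. The 150-day window is 150/29.08 = 5.2 to 150/22.73 = 6.6 half-lives. Day 157 is 156 days after dosing and covers both.

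**The case against.** The strongest reply is that the intent is already visible. The permissions in Section 6.8 make most sense if use during the study is otherwise restricted, and leaving live vaccines out of the post-discharge COVID-19 permission would be pointless if live vaccines were acceptable then. Intent can fairly be inferred, but neither passage is an instruction. The limited-use sentence reaches nonprescription medication only, and the sub-bullet governs COVID-19 vaccines only.

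Second, the consent document or Investigator's Brochure may contain the rule, and Section 5.1, criterion 6, binds participants to restrictions in the consent document. That stands as a limit on this point, which concerns the protocol as written.

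Third, safeguards exist: concomitant treatment is asked about at each visit, viral surveillance includes varicella-zoster, and adverse events are collected for at least 150 days. These detect exposure or infection after the fact and do not prevent it. Section 8.2.8 also warns that surveillance results may be delayed.

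Fourth, the numbers show presence of drug, not danger. This is correct. The six-week levels of 34 to 55 µg/mL are only about 10 to 17% of a 900 mg Cmax of roughly 320 µg/mL. The comparator regimen comes from a study judged generally well tolerated with no serious events, and the infections reported there as more frequent were mild.

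Finally, the 150-day window is defined for reproductive risk and does not automatically carry over to vaccines. This is a fair point about the length of a ban, not about whether one is needed.

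**Conclusion.** The point holds. As written, a non-COVID live vaccine after Day 5 discharge is not expressly permitted, but no stated rule prohibits it. Drug exposure is then substantial: roughly 40 to 70% of Cmax at discharge across the terminal-phase and two-compartment estimates, and tens of µg/mL at six weeks after 900 mg. It falls to a few per cent or less by 150 days.

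The exposure figures rest on pharmacokinetics from non-Japanese healthy participants, on dose proportionality, and for one route on an assumed inter-compartment clearance. They cannot be turned into an infection risk, because the documents give neither a concentration-effect relation nor a vaccination rate. This is a gap in participant protection worth closing. It does not affect the validity of the trial's analyses.

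**What to change.** Add one sentence to Section 6.8, cross-referenced from criterion 12, stating that live or attenuated live vaccines are prohibited from dosing through the Day 157 visit. Put a matching line in the consent document, or confirm that one is already there. Leave the permission for non-live COVID-19 vaccines after discharge unchanged.

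Day 157 is proposed because it needs no new visit and covers both five half-lives and the existing 150-day window. If the clinical team prefers a shorter ban, it should run for at least five half-lives, which is 145 days at the longer stated half-life, with the reason given.

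The cost is a sentence in each document, and participants put off elective live vaccination for about five months.
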